2.1 Background

Shoulder pain is a very common symptom. It has been reported that approximately 15 patients per 1000 present to their GP with shoulder pain every year ¹. Shoulder pain, inflammation and difficulty performing overhead activities are some of the symptoms associated with subacromial pathology ². Injections are a very common treatment for subacromial pathology ³. These injections are given by general practitioners, physiotherapists, rheumatologists and orthopaedic surgeons ⁴⁻⁶. If we can identify factors that improve the efficiency of these injections then this will be of great value. Previous studies have looked at the accuracy of various approaches for injections in terms of where the needle tip is and where the local anaesthetic is administered ⁷⁻¹⁰. However, there has been no previous study, to our knowledge, that has examined the clinical outcome of the various approaches.

2.2 Study Objectives

The aim is to determine if there is any difference in the effectiveness of a steroid injection, given for Shoulder Subacromial Pain Syndrome, when it is administered via an anterolateral as compared to a posterior approach. Here effectiveness is measured in terms of improvement in pain and function.

Primary outcome is improvement in the modified Oxford Shoulder Score at 3 months post-injection.

Our hypothesis is that there is no difference in improvement of pain with an injection given via an anterolateral approach compared to posterior approach.

3 Study Design

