[name]

PERSONAL EMAIL: [contact]

NHS EMAIL: [contact]

[contact]

MR [name]

SPECIALIST REGISTRAR

MERSEY DEANERY, [name],
[name]

PERSONAL EMAIL: [contact]

NHS EMAIL: [contact]

[contact]

MR [name]

CONSULTANT ORTHOPAEDIC SURGEON

BLACKPOOL VICTORIA HOSPITAL, [name]

[name]

PERSONAL EMAIL: [contact]

NHS EMAIL: [contact]

NHS [contact]

NHS [contact]

[contact]

1 Study Summary

Title	Subacromial Injections for Shoulder Subacromial Pain Syndrome – Comparing Anterolateral Versus Posterior Approach
Short Title	Anterolateral Versus Posterior Approach With Steroid Injection For Subacromial Pain Syndrome
Version & Date	Version six, 27 th March 2019
Chief Investigator	Mr [name]
Objectives	To determine if there is any difference in terms of pain relief in patients with shoulder subacromial pain syndrome, when given a steroid injection into the subacromial space via an anterolateral approach compared to a posterior approach.
Hypothesis	That there is no difference in terms of pain relief at 3 months, 6 months and 1 year from an injection via an anterolateral approach compared to one from a posterior approach

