3.2 Primary Study Endpoints

Primary end point will be improvement in Oxford Shoulder Score at 3 months post-injection

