3.8 Informed Consent

Informed consent will be obtained during the initial clinic visit after the patient has had adequate time to read the information leaflet, digest the information provided and ask any questions they may have, as well as express their views/wishes. The patient will be asked to sign a consent form indicating they have understood all aspects of the study and their rights. This form will also be signed by the researcher and three copies of this form will be obtained (one for patient, one for researchers which will be stored in the study site file and one for the clinical notes).

Withdrawal of Subjects

Patient will be free to withdraw from the study at any time without explanation and without prejudice. A patient will be withdrawn from the study, if unable to tolerate the injection or does not comply with physiotherapy. Abrupt termination of patient from study will not put the patient at risk. The patient will still be offered care as they would be routinely, if unable to continue in study for whatever reason.

If patient fails to attend the follow up clinic visit then a letter will be sent to the patient and copied to the GP as is done routinely when a patient does not attend. A follow up appointment will then be booked for the nearest possible date.

4 Prior and Concomitant Therapy

There are no restrictions to prior or concomitant medicines permitted during the study.

The only therapy that patients will receive will be physiotherapy.

5 Laboratory Assays

Not applicable

6 Study Procedures

All relevant procedures are detailed above.

7 Statistical Plan

The study statistician has calculated the number of participants needed for the study, so that the study can reliably answer its aims, whilst avoiding wastage of time and resources. Statistical methods have been used for sample size calculation as follows: the standard deviation for change in Oxford Shoulder Score (OSS) at 12 weeks from baseline was obtained from a previous study of steroid injection for shoulder pain (Holt, TA et al[11]). 43 patients in each group are needed based on 80% power for a two sample t-test, detecting a minimal important difference of 6 and a two-tailed significance level of 0.05 with a standard deviation of 9.1. This accounts for 10% attrition between baseline and 3 months as documented in the previous study (Holt, TA et al[11]).

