Baseline demographic and clinical variables will be reported using summary statistics. In terms of the primary outcome, the change in total Oxford Shoulder Score from baseline to 3 months post-injection will be compared between the two groups using either the Independent Samples t-Test or Mann-Whitney U Test, with the final choice depending on an exploration of the data. The same approach will be adopted for secondary outcomes. All analysis will be performed according to the intention to treat principle.

8 Safety and Adverse Events

There is no deviation in normal practice with regards to the medication being given, therefore standard pharmacovigilance procedures will be used.

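### The hypothesis is stated as no difference, but the plan has only a two-sided difference test and no confidence interval or rule for reading a non-significant result

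*Combined protocol and SAP*

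**What the plan says.** The hypothesis appears twice. Section 2.2 has: "Our hypothesis is that there is no difference in improvement of pain with an injection given via an anterolateral approach compared to posterior approach". The Study Summary has: "That there is no difference in terms of pain relief at 3 months, 6 months and 1 year from an injection via an anterolateral approach". Both concern pain, and the second covers three time points.

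The aim, also in section 2.2, is framed differently: "The aim is to determine if there is any difference in the effectiveness of a steroid injection".

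The primary endpoint is on another scale: "Primary end point will be improvement in Oxford Shoulder Score at 3 months post-injection" (section 3.2).

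Section 7 sizes the trial to detect a difference: "43 patients in each group are needed based on 80% power for a two sample t-test, detecting a minimal important difference of 6". It uses a two-tailed 0.05 level, an SD of 9.1 and 10% attrition. For the analysis, 3-month change in OSS "will be compared between the two groups using either the Independent Samples t-Test or Mann-Whitney U Test", with the choice made after looking at the data. For everything else, "The same approach will be adopted for secondary outcomes".

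No confidence interval for the between-route difference, no margin and no rule for a non-significant result appear anywhere. The 6-point figure is used only in the sample size statement.

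**The concern.** A test of no difference can reject that statement but cannot support it. When the hypothesis is itself worded as no difference and no other rule is given, the only planned result that could be taken to agree with it is p > 0.05. At this sample size, that p-value often goes with data that still allow a difference the trial itself calls important.

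Section 13 says that the results will be used to influence future care. A report that the two routes do not differ could therefore affect practice when the data have not ruled out a 6-point advantage for one of them.

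**Working it through.** **Inputs, all from section 7:** difference 6, SD of change 9.1, two-sided alpha 0.05, power 80%, attrition 10%, 43 per arm.

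**1. Reproduce the sample size.** With the noncentral t distribution, power is 79.9% at 37 per arm and 81.0% at 38. So 38 evaluable are needed, and 38 / 0.90 = 42.2, which rounds up to 43. The stated figure is correct for a superiority test.

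**2. Precision at 38 evaluable per arm.**
- SE = 9.1 × √(2/38) = 2.09
- 95% CI half-width = t(0.975, 74) × SE = 4.16

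**3. Which non-significant results leave 6 points open.** A result is non-significant if the observed difference is below 4.16 in absolute value. Its 95% CI reaches 6 if the observed difference exceeds 6 − 4.16 = 1.84. So:
- below about 1.84: non-significant, and 6 is excluded;
- about 1.84 to 4.16: non-significant, and 6 is not excluded. For example, an observed 3.0 gives 3.0 ± 4.16, or −1.2 to 7.2.

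**4. How often this happens.** Simulation with the SD re-estimated in each trial, 38 per arm, 400,000 runs per row:

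| True difference | Non-significant | Non-significant and 95% CI reaches 6 | Share of non-significant results | 95% CI wholly within ±6 |
|---|---|---|---|---|
| 0 | 95.0% | 32.9% | 35% | 62.1% |
| 3 | 70.5% | 42.2% | 60% | 28.3% |
| 4 | 52.6% | 37.3% | 71% | 15.2% |
| 6 | 19.1% | 16.6% | 87% | 2.5% |

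The last row shows what an interval rule gains. With a true 6-point difference, p > 0.05 occurs in 19.1% of trials, but an interval wholly within ±6 occurs in only 2.5%.

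**5. Sensitivity to attrition.** With all 43 per arm evaluable, the half-width is 3.90 and the band runs from 2.10 to 3.90. The shares at true differences of 0, 3 and 6 are then 25%, 52% and 83%. The chance of an interval within ±6 under equal routes is 71%. The pattern is the same.

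**The case against.** The strongest reply is that the hypothesis is simply the statistical null. The aim in section 2.2, the objective in the Study Summary and the GP letter in Appendix 5 all ask whether there is any difference. The Background hopes to find factors that make these injections work better. Aim, sample size and test agree with one another, and a two-sided test has no difference as its null. The 19% is only the type II error accepted by planning for about 80% power. This stands, and it means that neither the test nor the sample size is in error.

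A reader might infer more: that the investigators will treat p > 0.05 as confirming their hypothesis, or that this is an equivalence trial run with the wrong test. The documents support neither inference. No passage says how a non-significant result will be read, and no passage describes an equivalence aim. For scale, an equivalence design with a margin of 6 (an assumption, since the plan sets no margin), a true difference of 0 and 80% power would need 46 per arm with a 90% CI or 56 with a 95% CI, after 10% attrition. The plan makes no such claim and need not be held to those numbers.

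It would also be too strong to say that any non-significant result leaves 6 points possible. If the routes are truly equal, about 65% of non-significant results exclude it.

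Finally, the hypothesis concerns pain while the 6-point threshold concerns the OSS, and no threshold for the pain scale is given. A rule based on 6 points can therefore serve only the primary endpoint.

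What remains after all this is that section 7 gives no guidance for a non-significant result under either reading of the hypothesis.

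**Conclusion.** The point holds as a gap in wording and interpretation. The superiority test and the 43 per arm are sound. The hypothesis is worded as the conclusion that a non-significant result could be taken to support, and the plan provides neither an interval nor a rule to check that reading against its own 6-point threshold.

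The size depends on the truth. Between about 35% (routes equal) and 87% (true difference of 6) of non-significant results would have a 95% CI that does not exclude 6 OSS points. These figures assume the plan's SD of 9.1, 38 evaluable per arm, roughly normal change scores and a comparison of means. A larger SD or greater attrition would widen the band. The conclusion applies to 3-month OSS only; nothing comparable can be computed for pain from the documents.

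**What to change.** In section 2.2 and the Study Summary, restate the hypothesis as the null of a two-sided superiority comparison of 3-month OSS change between the two routes.

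In section 7, add:

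> The between-route difference in mean 3-month OSS change will be reported with its 95% CI whichever test is used. A non-significant result will not be reported as no difference. An important difference on the OSS will be described as excluded only if the 95% CI lies wholly within −6 to +6; otherwise a non-significant result will be reported as inconclusive.

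Confine the rule to the primary OSS endpoint, and do not present the trial as an equivalence trial. Fix the wording before any outcome data are examined.

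The cost is a few sentences and one less favourable figure to disclose beside the 80% power: at the planned size and with truly equal routes, the interval would exclude 6 points in only about 62% of trials. The sample size and patient care do not change.

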3.1.1 General

The study will be a randomised controlled trial.

Estimated duration is 36 months (12-18 months for patient recruitment, 12 months for follow up and data collection and analysis, 6 months for write up and publication).

1. Prior to injection: assessment of pain using a visual analogue score, clinical assessment of shoulder movement and completion of a modified Oxford Shoulder Score, Disabilities of Shoulder, Arm and Hand questionnaires and Short Form 36 Health Survey.
2. 20-30 minutes Post injection: assessment of pain using a visual analogue score

3. Prior to leaving hospital: pain experienced during the administration of the injection and the overall satisfaction with the injection
4. 3 months post injection: assessment of pain using a visual analogue score, clinical assessment of shoulder movement and completion of a modified Oxford Shoulder Score, Disabilities of Shoulder, Arm and Hand questionnaires and Short Form 36 Health Survey.
5. 6 months and 1 year post injection: assessment of pain using visual analogue score and completion of a modified Oxford Shoulder Score, Disabilities of Shoulder, Arm and Hand questionnaires and Short Form 36 Health Survey via post.

Hard copies of data (questionnaires and forms) collected will be placed into the patient's notes. At the same time this data will be recorded electronically on an Excel database and saved on an encrypted, password protected memory stick. This memory stick will be stored in a locked filing cabinet in the orthopaedic department at Blackpool Victoria Hospital. Please note: The electronic data will contain NO identifiable information. Participants will be identified by a unique predetermined study I.D number which can only be linked to them by members of the research team.

3.2 Primary Study Endpoints

Primary end point will be improvement in Oxford Shoulder Score at 3 months post-injection

3.3 Secondary Study Endpoints

Secondary end points include Oxford Shouldr Score (OSS) at 6 months and 1 year, pain on visual analogue scale at 3 months, 6 months and 1 year, Disabilities of Arm, Shoulder and Hand (DASH) questionnaire at 3 months, 6 months and 1 year and Short Form 36 (SF36) Health Survey at 3 months, 6 months and 1 year.

3.4 End of study

Total duration of the study will be 36 months. This includes participant selection, data collection/analysis and publication of findings. For each participant the duration of participation will be 1 year.

3.5 Subject Selection and Withdrawal

Subjects will be identified on presentation to the orthopaedic outpatient clinic of [name]. Patients will be free to withdraw from the study at any time without prior warning and without prejudice, participation will be entirely voluntary. Patients will be asked to sign a consent form indicating they have understood this.

3.5.1 Inclusion Criteria

1	Patient diagnosed with shoulder subacromial pain syndrome
2	Age \geq 18
3	Capacity to give valid consent for participation
4	Able to complete the follow up

3.5.2 Exclusion Criteria

1	Age $<$ 18
2	Lacking capacity/unable to give valid consent for participation

3	Full thickness rotator cuff tear diagnosed on either Ultrasound scan or Magnetic Resonance Imaging
4	Unable to complete follow up
5	Unable to speak or read English

3.6 Subject Recruitment and Screening

Potential study subjects will be assessed by a trained clinician in the Orthopaedic outpatient clinic, where a diagnosis of Shoulder Subacromial Pain Syndrome will be made. Information on the study will be given to the patients in the form of a leaflet and verbal explanation by the consultant. They will be allowed to read and digest the information for as long as required as well as ask any questions they may have before agreeing to take part.

No vulnerable groups will be involved.

3.7 Randomisation Process

Patients will be randomised by the selection of sealed envelopes with one of the two approaches listed inside. There will have 86 envelopes, 43 containing the anterolateral approach and 43 containing the posterior approach. The envelopes will be generated in advanced by the research team and will be unidentifiable once sealed. They will be allocated at random to the 86 participants. The envelopes will be kept in a locked filing cabinet in the orthopaedic department and once opened, the contents will be filed in the patients notes.

3.8 Informed Consent

Informed consent will be obtained during the initial clinic visit after the patient has had adequate time to read the information leaflet, digest the information provided and ask any questions they may have, as well as express their views/wishes. The patient will be asked to sign a consent form indicating they have understood all aspects of the study and their rights. This form will also be signed by the researcher and three copies of this form will be obtained (one for patient, one for researchers which will be stored in the study site file and one for the clinical notes).

Withdrawal of Subjects

Patient will be free to withdraw from the study at any time without explanation and without prejudice. A patient will be withdrawn from the study, if unable to tolerate the injection or does not comply with physiotherapy. Abrupt termination of patient from study will not put the patient at risk. The patient will still be offered care as they would be routinely, if unable to continue in study for whatever reason.

If patient fails to attend the follow up clinic visit then a letter will be sent to the patient and copied to the GP as is done routinely when a patient does not attend. A follow up appointment will then be booked for the nearest possible date.

4 Prior and Concomitant Therapy

There are no restrictions to prior or concomitant medicines permitted during the study.

The only therapy that patients will receive will be physiotherapy.

5 Laboratory Assays

Not applicable

6 Study Procedures

All relevant procedures are detailed above.

7 Statistical Plan

The study statistician has calculated the number of participants needed for the study, so that the study can reliably answer its aims, whilst avoiding wastage of time and resources. Statistical methods have been used for sample size calculation as follows: the standard deviation for change in Oxford Shoulder Score (OSS) at 12 weeks from baseline was obtained from a previous study of steroid injection for shoulder pain (Holt, TA et al[11]). 43 patients in each group are needed based on 80% power for a two sample t-test, detecting a minimal important difference of 6 and a two-tailed significance level of 0.05 with a standard deviation of 9.1. This accounts for 10% attrition between baseline and 3 months as documented in the previous study (Holt, TA et al[11]).

Baseline demographic and clinical variables will be reported using summary statistics. In terms of the primary outcome, the change in total Oxford Shoulder Score from baseline to 3 months post-injection will be compared between the two groups using either the Independent Samples t-Test or Mann-Whitney U Test, with the final choice depending on an exploration of the data. The same approach will be adopted for secondary outcomes. All analysis will be performed according to the intention to treat principle.

8 Safety and Adverse Events

There is no deviation in normal practice with regards to the medication being given, therefore standard pharmacovigilance procedures will be used.

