1.1 Flowchart of Treatment Schedule

- STEP 1 - New diagnosis of Shoulder Subacromial Pain Syndrome

Patient presents to orthopaedic outpatient clinic and is diagnosed as having shoulder subacromial pain syndrome, offered and agrees to have a steroid injection

- STEP 2 – Does patient meet inclusion criteria?

NO – does not enter study

[figure not shown]
YES – patient initiated to enter study

[figure not shown]
- STEP 3 – Patient consent and study schedule

Patient agrees and consents – patient participates in study. They will be seen in outpatient clinic approximately 3 months following the injection. Postal questionnaires will be sent out at 6 months and 1 year.

Patient does not agree or consent – patient does not enter study

- Please see flow chart below

2 Overview

Patients who present with subacromial pain syndrome (disorders such as subacromial bursitis, rotator cuff tendinopathy, calcific tendinitis, subacromial inflammation with a partial thickness rotator cuff tear) to the orthopaedic outpatient clinic are treated initially with a subacromial steroid injection in addition to physiotherapy for a period of 3 months. This applies to patients who have had no other treatments previously as well as to patients who have had previous physiotherapy or steroid injections prior to presentation. Patients who do not want to undergo the treatment offered are either treated with simple analgesia, sole physiotherapy or surgery.

When a patient with one of the above conditions agrees to go ahead with a steroid injection followed by physiotherapy, the steroid injection is given at the earliest opportunity. The steroid injection is given into the subacromial space either using the anterolateral (front-side) approach (1 cm below and behind the anterior edge of the acromion with the needle aiming towards the under surface of the acromion) or using the posterior (back-side) approach (1cm inferior and medial to the posterolateral acromial edge with the needle pointing towards the anterolateral aspect of the acromion). The exact approach is determined according to the preference of the person carrying out the injection. As a routine we use a 10ml syringe containing 10mls of 0.25% Marcaine along with 40mg triamcinolone with an 18 gauge (green) needle. It is normal for patients to complain of some discomfort during the injection. If a patient experiences any significant discomfort or they

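### A missed 3-month visit, where the primary OSS is collected, leads only to a letter and a rebooking with no limit on delay; the forms posted at 6 and 12 months could be posted then too

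*Combined protocol and SAP*

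**What the plan says.** Section 3.2 fixes the time point: "Primary end point will be improvement in Oxford Shoulder Score at 3 months post-injection". Section 7 (Statistical Plan) makes the analysis variable the same: "the change in total Oxford Shoulder Score from baseline to 3 months post-injection will be compared between the two groups".

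The 3-month assessment is a clinic visit, which section 1.1 and section 2 (Overview) place at roughly 3 months without a window in days or weeks. The Withdrawal of Subjects text under section 3.8 covers non-attendance. A letter goes to the patient, with a copy to the GP, as in routine care. Then: "A follow up appointment will then be booked for the nearest possible date". No maximum delay, second-miss step or other way of obtaining the questionnaire is given.

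For the later time points section 1.1 says: "Postal questionnaires will be sent out at 6 months and 1 year". Section 2 lists the posted forms as OSS, visual analogue pain, DASH and SF36, which are the questionnaires used at 3 months. Section 12.1 includes envelopes and postage for follow-up questionnaires in the approved funding.

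Section 7 states that all analysis follows intention to treat, but gives no rule for a 3-month score that is late or missing.

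**The concern.** Two things can happen to a patient who misses the visit.

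- **The form is completed late.** Each of the 12 OSS items on the follow-up questionnaire asks about the preceding four weeks. A form completed at, say, 5 months describes months 4 to 5. The plan does not say whether that score counts as the 3-month value.
- **The form is never completed.** A patient who does not re-attend has no primary outcome, even if he or she would have filled in a posted questionnaire.

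At stake are the timing of the primary measurement and the number of patients who contribute to it. Selection is also possible. Section 2 says that improved patients need no further intervention at 3 months, while those still troubled discuss further treatment, so the reason to attend may depend on symptoms.

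**Working it through.** **Inputs (section 7).** Difference: "detecting a minimal important difference of 6". Significance level and SD: "a two-tailed significance level of 0.05 with a standard deviation of 9.1". Size and test: "43 patients in each group are needed based on 80% power for a two sample t-test". Attrition to 3 months: 10%. Allocation is 43 per arm, 86 in total (section 3.7).

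**Step 1: reproduce the plan's figure.** The standardised difference is 6 / 9.1 = 0.659. A two-sample t-test with two-sided alpha 0.05 and 80% power (noncentral t) needs 37.09, so 38 evaluable patients per arm. Allowing for 10% loss, 38 / 0.9 = 42.2, so 43 per arm. The stated sample size reproduces exactly.

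**Step 2: power by share of patients without a usable 3-month OSS.** With n evaluable per arm, the noncentrality parameter is (6 / 9.1) × √(n / 2) on 2n − 2 degrees of freedom. At n = 38.7 this is 0.659 × √19.35 = 2.90. The documents give only the 10% figure; the other rows are assumptions.

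| Loss | n per arm | Power |
|---|---|---|
| 0% | 43 | 85.6% |
| 5% | 43 × 0.95 = 40.85 | 83.7% |
| 10% (planned) | 43 × 0.90 = 38.7 | 81.7% |
| 15% | 43 × 0.85 = 36.55 | 79.4% |
| 20% | 43 × 0.80 = 34.4 | 76.9% |

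**Step 3: the margin.** Power reaches 80% at 37.09 per arm, so the break-even loss is 1 − 37.09 / 43 = 13.7%, or about 14%. In whole patients, 38 per arm gives 81.0% and 37 gives 79.9%. The trial can therefore lose 43 − 38 = 5 primary outcomes per arm and stay above 80%.

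**Step 4: what posting could recover.** The planned loss is 0.10 × 86 = 8.6 patients. If half of them were missed visits recovered by post, the loss would be 5% and power 83.7%. If all were, power would be 85.6%. The second figure is a ceiling, because some attrition will be withdrawal rather than a missed visit.

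**Step 5: compare the two collection routes.**

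| | 3 months (primary) | 6 and 12 months (secondary) |
|---|---|---|
| Route | Clinic visit | Post |
| OSS, VAS, DASH, SF36 | Yes | Yes |
| Needs a clinician | Shoulder movement and management form only | No |
| If no response | Letter and rebooking, no time limit | Nothing stated |

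The primary score is among the items that do not need the visit, yet rebooking the visit is the only stated way to recover it.

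**The case against.** The strongest reply is that the plan has already paid for this loss. The sample size includes 10% attrition, power after that loss is above target, and nothing in the documents suggests that loss will be higher. That stands: posting the forms adds 2 to 4 percentage points to an adequate figure.

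The recovery figures are also soft. Section 3.8 gives other routes out of the study: voluntary withdrawal, not tolerating the injection, and not complying with physiotherapy. Forms posted to non-attenders recover none of these, and the documents give no split. That stands too, and is why the figures are labelled as an assumption and a ceiling.

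A reader might infer that the primary endpoint has the weakest collection route in the trial. The documents do not support this. At 3 months staff are on hand to help and a missed visit triggers a letter and a rebooking, whereas no reminder is stated for the postal forms. No response rates are given for either route.

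A reader might also infer that the comparison is biased. The follow-up rule is the same in both arms, and nothing shows that attendance or delay differs by approach. Bias is possible but not shown, and its direction and size cannot be derived from the plan.

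Finally, the wording of the rebooking rule does intend promptness, and rebooking remains necessary for the clinical assessment. Neither point supplies a limit on delay or a second way to obtain the OSS.

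**Conclusion.** The concern holds as a gap in how the primary outcome is recovered after a missed visit. It applies to non-attenders only, and their number is unknown. For them, the plan offers a letter and an open-ended rebooking, while a suitable and funded postal route is used only for later time points.

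It might be read as showing an underpowered trial. It does not: 43 per arm reproduces, and planned loss leaves 81.7% power. The power gain from the change is at most 85.6 − 81.7 = 3.9 percentage points, and that requires the whole planned loss to be recoverable by post. The better reasons for the change are that the primary score is measured at the intended time and that fewer patients lack it. All power figures assume a difference of 6, an SD of 9.1 and equal loss in the two arms.

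The absent visit window is, taken alone, mostly missing detail. The postal fallback is the substantive improvement, and it is worth making because it costs so little.

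**What to change.** 1. When a patient misses the 3-month visit, post the OSS, VAS, DASH and SF36 pack at that time, with one reminder. Keep the rebooked visit for shoulder movement and the clinician's form.
2. Have the sponsor choose and state a window for the 3-month score, applied through the date field already on the follow-up questionnaire.
3. Keep scores completed after the window in the intention-to-treat analysis, and add a sensitivity analysis restricted to in-window scores. Excluding late forms from the main analysis would discard observed primary outcomes and sit badly with the intention-to-treat statement.

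The cost is a few sentences in the protocol and, at the planned loss rate, up to about 9 extra packs (0.10 × 86 = 8.6) plus any reminders, against up to 86 × 2 = 172 already planned. The downside is that a few primary scores would be completed at home rather than in clinic. The required sample size does not change.
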